#### **Association between infection and neutropenia/lymphopenia**

Depending on the number of cases with CTCAE Grade 2 or greater, a summary table will be provided for treatment-emergent infections that were preceded or accompanied by neutropenia. For this analysis, neutropenia is defined as (1) CTCAE Grade 2 or greater, (2) Grade 3 or greater. Infection events with onset date  $\leq 14$  days before or after the Grade 2 or greater neutrophil count collection date will be considered as infections preceded or accompanied by neutropenia.

Similar analyses as above will be conducted to evaluate the association between infection and lymphopenia.

#### **6.15.5.7. Major Adverse Cardiovascular Events (MACE) and Other Cardiovascular Events**

Potential major adverse cardiovascular events (MACE) and other cardiovascular events requiring adjudication will be analyzed.

Categories and subcategories analyzed will include, but are not limited to, the following:

- MACE
  - Cardiovascular death,
  - Myocardial infarction (MI),
  - Stroke,
- Other cardiovascular events
  - Transient ischemic attack,
  - Hospitalization for unstable angina,
  - Hospitalization for heart failure,
  - Serious arrhythmia,
  - Resuscitated sudden death,
  - Cardiogenic shock,
  - Coronary interventions (such as coronary artery bypass surgery or percutaneous coronary intervention),
- Non-cardiovascular death,
- All-cause death.

In general, events requiring adjudication are documented by investigative sites using an endpoint reporting CRF. This CRF is then sent to the adjudication center for external adjudication which uses an adjudication reporting CRF to document the final assessment of the event as a MACE, as some other cardiovascular event, or as no event (according to the Clinical Endpoint Committee Charter). In some cases, however, the investigator may not have deemed that an event had met the endpoint criteria but the event was still sent for adjudication as a potential MACE, other cardiovascular event, or no event. These events are included in the adjudication process to ensure adequate sensitivity. In these instances, the adjudication reporting CRF will not have a matching endpoint reporting CRF from the investigator. Events generated from these

circumstances will be considered as events sent for adjudication in the absence of an investigator's endpoint reporting form.

The number and percentage of patients with MACE, other cardiovascular events, non-cardiovascular death, and all-cause death, as positively adjudicated, will be summarized by treatment group based on the categories and subcategories above.

A listing of the events sent for adjudication will be provided to include data concerning the MedDRA PT related to the event, the seriousness of the event, and the event outcome, along with the adjudicated result.

#### **6.15.5.8. Venous and Pulmonary Artery Thromboembolic (VTE) Events**

Events identified as representative of venous thromboembolic events (VTE) disease will be classified as Deep Vein Thrombosis (DVT), pulmonary embolism (PE), or other peripheral venous thrombosis and will be analyzed. The following definitions apply:

- DVT: Clinical diagnosis of a thrombosis in a deep vein above the knee that must be confirmed by objective evidence of either: a filling defect of deep veins of the leg on venography or a non-compressible venous segment on ultrasound or confirmation by other imaging modality (e.g., Computed tomography [CT], Magnetic Resonance Imaging [MRI]).
- PE: Clinical diagnosis of pulmonary embolus that must be confirmed by objective evidence of either: a filling defect of pulmonary arteries by either pulmonary angiography or CT angiography or by a high probability Ventilation Perfusion (VQ) scan.
- Other Peripheral Venous Thrombosis: Clinical diagnosis of a venous thrombosis not specified by either DVT or PE above. Other peripheral venous thrombosis disease must be confirmed by objective evidence by imaging including venography, ultrasound, CT scan, or MRI. Examples of these would include non-superficial below knee thrombosis, portal vein, subclavian vein, or mesenteric vein. Superficial thrombophlebitis alone is not considered a VTE event.

In general, events requiring adjudication are documented by investigative sites using an endpoint reporting CRF. Refer to Section 6.15.5.7 for more details as the process is the same as that of MACE.

The number and percentage of patients with a VTE, DVT/PE, DVT, PE, and other peripheral venous thrombosis, as positively adjudicated, will be summarized by treatment group. Note that the below knee thrombosis captured in the "other peripheral venous thrombosis" category will be summarized within DVT.

A listing of the VTE events sent for external adjudication will be provided to include data concerning the MedDRA PT related to the event, the seriousness of the event, and the event outcome, along with the adjudicated result.

### 6.15.5.9. Arterial Thromboembolic (ATE) Events

Refer to the Compound level safety standards.

### 6.15.5.10. Malignancies

Malignancies will be identified using terms from the malignant tumors SMQ (SMQ 20000194). Malignancies excluding non-melanoma skin cancers (NMSC) and NMSC will be reported separately.

All the cases identified by malignant tumors SMQ will be assessed through medical review to determine confirmed NMSC cases.

First, a listing including all the malignancy cases will be prepared before database lock along with the *planned* NMSC flag according to the current MedDRA version PTs (the list will be updated depending on the MedDRA version used for analysis):

- Squamous cell carcinoma of skin (10041834)
- Bowen's disease (10006059)
- Basal cell carcinoma (10004146)
- Basosquamous carcinoma (10004178)
- Basosquamous carcinoma of skin (10004179)
- Squamous cell carcinoma (10041823)
- Skin squamous cell carcinoma metastatic (10077314)
- Skin cancer (10040808)
- Carcinoma in situ of skin (10007390)
- Keratoacanthoma (10023347)
- Vulvar squamous cell hyperplasia (10079905)
- Skin squamous cell carcinoma recurrent (10081136)

This internal review is to occur prior to database lock. The case review and subsequent summary analyses will include all the cases reported in the study database or by LSS report, disregarding the length of gap between the last treatment dose date and the event date. The NMSC flag will be confirmed during the internal review process.

The number and percentage of patients with TEAEs associated malignancies excluding NMSC and NMSC will be summarized by treatment group.

### 6.15.5.11. Allergic Reactions/Hypersensitivities

A search will be performed using the MedDRA version 21.1 SMQs to search for relevant events, using the following queries:

- Anaphylactic reaction SMQ (20000021)
- Hypersensitivity SMQ (20000214)
- Angioedema SMQ (20000024)

Assessment of the Anaphylactic reaction SMQ includes an algorithmic query. The algorithmic approach comprises one or more events associated with an individual administration of study drug, where the events include:

- A narrow term from the SMQ (Category A of the SMQ);
- Multiple terms from the SMQ, comprising terms from at least two of the following categories from the SMQ:
  - Category B - (Upper Airway/Respiratory signs and symptoms)
  - Category C - (Angioedema/Urticaria/Pruritus/Flush signs and symptoms)
  - Category D - (Cardiovascular/Hypotension signs and symptoms).

Refer to the Compound safety level standards for details.

#### **6.15.5.12. Gastrointestinal Perforations**

Treatment-emergent adverse events related to potential gastrointestinal (GI) perforations will be analyzed using reported AEs. Identification of these events will be based on review of the PTs of the MedDRA SMQ 20000107, GI perforations (note that this SMQ holds only narrow terms and has no broad terms). Potential GI perforations identified by the above SMQ search will be provided as a listing for internal review. Each case will be assessed to determine whether it is GI perforation. A summary table based on medical review may be provided and treatment comparisons will be made using Fisher's exact test.

#### **6.15.5.13. Columbia Suicide Severity Rating Scale**

Suicidal ideation, suicidal behavior, and self-injurious behavior without suicidal intent, based on the C-SSRS, will be listed by patient and visit. Only patients that show suicidal ideation/behavior or self-injurious behavior without suicidal intent during treatment will be displayed along with all their ideation and behavior, even if not positive (i.e., if a patient's answers are all 'no' for the C-SSRS, then that patient will not be displayed). A summary of the C-SSRS categories during treatment and a shift summary in the C-SSRS categories from baseline during treatment will be provided. Refer to the Compound safety level standards for details.

#### **6.15.5.14. Self-Harm Supplement Form and Self-Harm Follow-up Form**

The Self-Harm Supplement Form is a single question to enter the number of suicidal behavior events, possible suicide behaviors, or nonsuicidal self-injurious behaviors. If the number of behavioral events is greater than zero, it will lead to the completion of the Self-Harm Follow-Up Form. The Self-Harm Follow-Up Form is a series of questions that provides a more detailed description of the behavior cases. A listing of the responses given on the Self-Harm Follow-Up Form will be provided.

### **6.16. Subgroup Analyses**

Subgroup analyses comparing each dose of baricitinib to placebo will be performed on the ITT population at Week 16 using the primary censoring rule for the following:

- Proportion of patients achieving IGA 0 or 1
- Proportion of patients achieving EASI75 Response Rate
- Proportion of patients achieving Itch NRS 4-point improvement

The following subgroups, categorized into disease-related characteristics and demographic characteristics, will be evaluated:

- Patient Demographic and Characteristics Subgroups:
  - Gender (male, female)
  - Age group (<65, ≥65 years old)
  - Age group (<65, ≥65 to <75, ≥75 to <85, ≥85 years old)
  - Baseline weight: (<60 kg, ≥60 to <100 kg, ≥100 kg)
  - Baseline BMI (<25 kg/m^2, ≥25 to <30 kg/m^2, ≥30 kg/m^2)
  - Race: (American Indian or Alaska Native, Asian, Black or African American, Native Hawaiian or Other Pacific Islander, White, Multiple)
  - Baseline renal function status: impaired (eGFR <60 mL/min/1.73 m^2) or not impaired (eGFR ≥60 mL/min/1.73 m^2)
- Geographic Region Subgroups:
  - Region: (as defined in [Table JAIY.5.1](#))
  - Specific regions (Europe, other)
  - Specific regions (East Asia[Korea, Japan and Taiwan], other)
  - Specific country (Japan, other)
  - Prior systemic therapy use (yes, no)
- Baseline Disease-Related Characteristics Subgroup
  - Baseline disease severity (IGA score): 3, 4

Descriptive statistics will be provided for each treatment and stratum of a subgroup as outlined, regardless of sample size. As all endpoints are categorical, subgroup analyses will be performed using logistic regression using Firth's correction to accommodate (potential) sparse response rates. The model will include the categorical outcome as the dependent variable and baseline value (for EASI and itch), baseline severity, treatment, subgroup, and treatment-by-subgroup interaction as explanatory variables. Missing data will be imputed using NRI (Section 6.4.1). The treatment-by-subgroup interaction comparing treatment groups will be tested at the 0.1 significance level. The p-value from the logistic regression model will be reported for the interaction test and the subgroup test, unless the model did not converge. Response counts and percentages will be summarized by treatment for each subgroup category. The difference in percentages and 95% CI of the difference in percentages using the Newcombe-Wilson without continuity correction will be reported. The corresponding p-value from the Fisher's exact test will also be produced.

In case any level of a subgroup comprises <10% of the overall sample size, only descriptive summary statistics will be provided for treatment arms, and no treatment group comparisons will be performed within these subgroup levels.

Additional subgroup analyses on efficacy may be performed as deemed appropriate and necessary.

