10.3. Statistical Analyses

10.3.1. General Statistical Considerations

Statistical analysis of this study will be the responsibility of Lilly or its designee. A detailed SAP describing the statistical methodologies will be developed by Lilly or its designee.

Any change to the data analysis methods described in the protocol will require an amendment ONLY if it changes a principal feature of the protocol. Any other change to the data analysis methods described in the protocol, and the justification for making the change, will be described in the clinical study report (CSR). Additional exploratory analyses of the data will be conducted as deemed appropriate.

All tests of treatment effects will be conducted at a 2-sided alpha level of 0.05, unless otherwise stated. Treatment comparisons of discrete efficacy variables between baricitinib and placebo will be made using a logistic regression analysis with region, disease severity, and treatment group in the model. The percentages, difference in percentages, and 95% confidence interval

(CI) of the difference in percentages will be reported. Treatment-by-region interaction will be added to the logistic regression model of the primary and key secondary variables as a sensitivity analysis. If this interaction is significant at a 2-sided 0.1 level, further inspection will be used to assess whether the interaction is quantitative (i.e., the treatment effect is consistent in direction but not size of effect) or qualitative (the treatment is beneficial for some but not all regions). The p-value from the Fisher exact test will also be produced.

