10.3.3. Efficacy Analyses

10.3.3.1. Primary Analyses

The primary efficacy measure is the binary outcome of response defined as IGA score of 0 or 1 (clear or almost clear skin) and ≥ 2 -point improvement from baseline at Week 16. Primary analysis will be conducted using a logistic regression as described above with treatment and the stratification variables (disease severity and region) in the model. Nonresponder imputation for missing data as described above will be used.

Additional analysis of the primary efficacy outcome will include analyzing the outcome as observed, that is, whether or not rescue medication was used.

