10.3.6.2. Subgroup Analyses

To assess whether the treatment effect is similar across subgroups for the primary efficacy outcome, a logistic model will be used and will include treatment, stratification variables, the subgroup variable (e.g., sex) and the subgroup by treatment interaction. If the interaction is statistically significant at $\alpha=0.10$, the nature of the interaction will be explored, that is, within each subgroup the treatment effect will be estimated. Similarly, for the continuous variables of EASI, the MMRM model will include additional variables for subgroup and the subgroup by treatment interaction.

Subgroups to be evaluated will include region, baseline severity, sex, age, race, prior therapy, etc. Further definitions for the levels of the subgroup variables, the analysis methodology, and any additional subgroup analyses will be defined in the SAP. As this study is not powered for subgroup analyses, all subgroup analyses will be treated as exploratory.

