### 6.3. Covariate Adjustment

The randomization to treatment groups at Week 0 (Visit 2) is stratified by disease severity (IGA) and geographic region as described in Section 5.1. Unless otherwise specified, the statistical analysis models will adjust for these stratification variables. The covariates used in the logistic model for categorical data will include the parameter value at baseline. The covariates used in the ANCOVA model for continuous data will include the parameter value at baseline. Inclusion of baseline in the model ensures treatment LSM are estimated at the same baseline value. When an MMRM analysis is performed, baseline value and baseline-by-visit interactions will be included as covariates.

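### The SAP's subgroup model leaves out region, contrary to the protocol's description, and two day-count t-tests leave out both strata; exploratory outputs only, minor

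*SAP*

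**What the plan says.** Protocol 10.3.6.2 specifies that, for the primary efficacy outcome, "a logistic model will be used and will include treatment, stratification variables, the subgroup variable" and the subgroup-by-treatment interaction. Protocol 10.3.3.1 names the strata in describing the primary model: "treatment and the stratification variables (disease severity and region) in the model". Protocol 7.2 gives the same two factors for randomisation.

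SAP 6.16 covers IGA 0/1, EASI75 and the 4-point itch response at Week 16. After a baseline value for EASI and itch, it lists "baseline severity, treatment, subgroup, and treatment-by-subgroup interaction as explanatory variables". Severity is there and region is not. The main categorical model in SAP 6.2.3 contains both. SAP 6.3 sets a general default: "Unless otherwise specified, the statistical analysis models will adjust for these stratification variables".

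SAP 6.16 continues: "The p-value from the logistic regression model will be reported for the interaction test and the subgroup test". The 0.1 level is attached to the interaction only. No hypothesis, contrast or level is given for the other test.

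SAP Table JAIY.6.7 compares itch-free and skin-pain-free days with a two-sample t-test. Days without background TCS (6.11.1) and PBI scores (footnote a of the same table) get an ANOVA on region, baseline severity and treatment.

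**The concern.** A trial that randomises within region and severity would normally keep both in its models, and the protocol says it will for this one. An explicit list that retains one stratum and drops the other, without a reason, lets two programmers build different models from the same SAP.

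Treatment is randomised, so leaving out region should do little to treatment contrasts. A subgroup factor is not randomised. Race is a listed subgroup and Japan is a whole region stratum, so race and region will overlap heavily. If the undefined test were a race main effect, regional differences in response could surface as a race p-value.

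For the two day-count outcomes the stake is smaller: adjustment that is already used for comparable outcomes is not used here.

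**Working it through.** **1. The plan's own figure.** The sample size sections (protocol 10.1, SAP 6.1) give 89% power for 30% against 10%, two-sided alpha 0.025, Fisher exact. The design sections give 100 patients per arm. Exact enumeration gives 89.1%, so the figure reproduces. Nothing below changes it; the subgroup sections state no power.

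**2. Model terms side by side.**

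| Source | Severity | Region |
|---|---|---|
| Protocol 10.3.3.1, primary model | yes | yes |
| Protocol 10.3.6.2, subgroup model | yes (as a stratum) | yes (as a stratum) |
| SAP 6.2.3, main model | yes | yes |
| SAP 6.3, default | yes | yes, unless specified otherwise |
| SAP 6.16, subgroup model | yes | not listed |

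**3. Where region can be added.** Let E, J and R indicate Europe, Japan and rest of world, so E + J + R = 1. Europe/other is E and Japan/other is J, so both are aliased with a three-level region factor. The grouping "Specific regions (East Asia[Korea, Japan and Taiwan], other" is not, because it splits R (Korea and Taiwan against Australia and Argentina). SAP 5.2 pools the two smallest strata if one has fewer than 30 patients. If Japan is pooled with rest of world, the region factor reduces to E: Europe/other is still aliased and Japan/other no longer is. In the IGA 3/4 subgroup, the listed severity term and the subgroup term are the same variable.

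**4. Effect of leaving out region (simulation, 6,000 trials per scenario).** From the documents: 3 × 100 patients, 10% placebo and 30% active response, Firth logistic model, interaction tested at 0.1. Assumed: regions 40/25/35%; IGA 4 in 45%, odds ratio 0.4; Asian share 2% in Europe, 99% in Japan and 30, 60 or 90% in rest of world; Japan response below Europe by the stated odds ratio, with rest of world midway on the log-odds scale; race as Asian/non-Asian; no true race effect; IGA 0/1 only.

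The race main effect is either averaged over arms, b_race + (b_race×2mg + b_race×4mg)/3, or b_race alone under placebo-reference coding. Rejection at 5% without region, at a 60% Asian share (range over 30–90%):

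| Japan–Europe odds ratio | Averaged over arms | Placebo reference |
|---|---|---|
| 1.5 | 10% (8–12%) | 2% (1–4%) |
| 2 | 24% (19–30%) | 4% (2–7%) |
| 3 | 52% (45–61%) | 7% (2–14%) |

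With region in the model the rate is 3–4% under either coding. With no regional difference it is 2–4% either way.

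Other outputs:
- Interaction test, nominal 10%: 6.6–8.0% without region, 6.7–8.2% with.
- Power for 4 mg against placebo within Asian patients: changes by at most 0.8 points (for example 52.3% against 53.0% at odds ratio 3, 60% share). Within non-Asian patients: at most 0.4.
- A separate simulation with a generic binary subgroup and a true interaction log-odds ratio of 1.0: power 36–40% without region, 37–39% with. The largest gap is 36.0% against 38.7%.

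**5. What adjusting costs.** Assume a true race odds ratio of 0.5 and no regional effect. Adding region cuts the power of the arm-averaged race test from 61% to 28% at a 60% Asian share, and from 58% to 15% at 90%. Runs with intercepts set to hold 10/30/30% response give 54% to 26% and 59% to 15%.

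**6. The t-tests.** The SE ratio is sqrt(1 − R²), where R² is the share of variance the covariates explain. Power from a nominal 80% becomes Φ((1.96 + 0.842)/sqrt(1 − R²) − 1.96). The documents give no R².

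| Covariates | R² (assumed) | SE reduction | Power |
|---|---|---|---|
| Strata only | 1% | 0.5% | 80.4% |
| Strata only | 3% | 1.5% | 81.2% |
| Strata + baseline NRS | 5% | 2.5% | 82% |
| Strata + baseline NRS | 10% | 5.1% | 84% |
| Strata + baseline NRS | 20% | 10.6% | 88% |

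**The case against.** **The protocol allows this.** It states that "the analysis methodology, and any additional subgroup analyses will be defined in the SAP". Section 10.3.1 reserves amendments for principal features; it sends "Any other change to the data analysis methods described in the protocol, and the justification for making the change" to the clinical study report. This stands. A reader might infer a protocol breach, but silence in the SAP is permitted, so the finding is only an unexplained mismatch.

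**SAP 6.3 brings region back.** Possible, but its default gives way to a different specification, and an explicit list naming one stratum and not the other reads as one. The text does not settle it.

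**The race result needs the less natural reading.** SAP 6.16 opens by describing comparisons of each dose with placebo and closes by restricting treatment comparisons within small subgroup levels. Protocol 10.3.6.2 speaks of estimating the treatment effect within each subgroup. These point to a within-level treatment comparison, which barely moves. This stands. A reader might take the 45–61% rates as the plan's false-positive risk. The documents do not support that: the figure needs the main-effect reading, arm-averaged coding and an assumed regional odds ratio of 3. The SAP also has six race categories, not two, and an unadjusted race association is a legitimate descriptive quantity.

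**Adjustment has a price.** It does for a true race association (step 5), because race and region nearly coincide under these assumptions.

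**The t-tests are a matter of preference.** They are valid as written, and calling them wrong would be unsupported. Adjustment is still cheap and matches what the SAP does for similar outcomes. Neither existing ANOVA contains a baseline score, so adding baseline NRS goes further than those precedents and could lose patients whose diary baseline is missing.

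**Conclusion.** The concern holds as a minor one. That region is missing from the SAP 6.16 list, against protocol 10.3.6.2, is certain on the text; whether SAP 6.3 was meant to restore it is not. The interaction test and the within-level treatment comparisons are essentially unaffected. The one route to a misleading result is a main-effect reading of an undefined p-value, and its size depends on coding and on region mix, race mix and regional effects that the documents do not give.

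Every affected output is exploratory. The primary and key secondary models do not change, and a reader should not infer any doubt about them. For the day-count outcomes the gain is precision only; the R² values above are illustrations, not estimates.

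**What to change.** **SAP 6.16**
- Add region, as pooled under 5.2, to the logistic model, except where the subgroup equals or is aliased with the region factor actually used. With three regions, the exceptions are Region, Europe/other and Japan/other; East Asia/other keeps region. Recheck the exceptions if strata are pooled.
- Enter severity once in the IGA 3/4 subgroup analysis.
- State that the subgroup test is the treatment comparison within each level. If it is the main effect, give its coding and label it prognostic.
- If region is left out on purpose, say why.
- Leave the Newcombe-Wilson intervals as they are.

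**SAP Table JAIY.6.7**
- Replace the two-sample t-tests for itch-free and skin-pain-free days with a model on treatment, region and baseline IGA severity, as in 6.11.1 and footnote a.
- Baseline Itch or Skin Pain NRS may be added for more precision. SAP 6.2.2 lets a diary baseline be missing, so a stated rule is then needed to keep those patients in the analysis.

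**Cost.** A few sentences of SAP wording and routine code, with no new data. The one statistical cost is lower power for a true race association if a race main effect is reported.
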